10.3 Intervention: AXR or AXR + BUS

Infants randomized to AXR arm will have a portable abdominal x-ray ordered, performed, and interpreted per usual clinical workflow. Likewise, infants randomized to AXR + BUS intervention will have both a portable abdominal x-ray and add-on BUS ordered, performed, and interpreted per usual clinical workflow. Results of all imaging tests (AXR or AXR + BUS depending on randomization) will be available to the care team taking care of infants as per usual clinical care.

10.4 Post-AXR and Post-BUS Survey

Neonatologists will receive surveys to determine changes in their clinical diagnostic and therapeutic thinking after results of AXR or AXR + BUS.

10.5 Cross-over

Infants randomized to AXR only, but for whom the treating neonatologist deems a BUS is clinically warranted, will be allowed to cross-over and have BUS ordered. In our pilot study, only one infant randomized to AXR arm “cross-over” to AXR + BUS arm because of clinical concerns for an abdominal abscess (abdominal abscess is best evaluated by sonography). We had no instances in our pilot study of cross-over besides this isolated event, indicating clinical equipoise between AXR vs AXR + BUS. As such, although allowed in the study we anticipate cross-over to be rare.

10.6 Follow-up imaging

Infants with suspected NEC may need additional follow-up imaging for ongoing concerns of NEC. If the treating neonatologist deems follow-up imaging is needed, study infants will continue to have either AXR or AXR + BUS performed as determined by their randomization arm.

10.7 Multiple episodes of NEC concern

Infants may also develop more than one episode of NEC concern during their admission. For such instances, study infants will remain in the same randomization arm throughout the study.

10.8 Diagnosis and treatment decisions

All other diagnostic testing will be decided upon independently according to the treating neonatologist's clinical judgment. All treatment decisions, including length of bowel rest and length of antibiotic treatment, will also be at the discretion of the treating neonatologist.

10.9 Blood and Other Specimen Collection: NA

11.0 Surveys and Psychometric Testing:

- We will conduct two surveys to determine change in clinician's diagnostic and therapeutic thinking. The first survey (post-AXR survey), applicable to all infants, will be conducted after AXR is performed. The second survey (post-BUS survey), applicable only to infants randomized to AXR + BUS, will be conducted after BUS is performed. Surveys will be answered by the neonatologist taking care of the infants using a 5-point Likert scale from "not at all likely" to "extremely likely".

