10.2 Randomization

Infants who meet inclusion criteria of NEC concern as above will be randomized to either AXR arm or AXR + BUS arm based on the calendar month the infant was born. A pre-generated randomization calendar will be posted in the NICU workroom to inform the care team which arm the infant will be randomized to, and consequently which imaging test will be ordered.

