28.0 Statistical Analysis*

28.1 We will use two-tailed McNemar's test with paired measures to analyze differences in diagnostic thinking efficacy and therapeutic efficacy from pre- and post-BUS surveys. Comparison of duration of antibiotics, bowel rest, and days to full enteral feeds will be performed using Student's t-test. Kaplan-Meier curve will be used to analyze time to full feeds between the 2 groups, censoring for death, discharge/transfer out of the hospital, or 30 days following initial NEC concern. Analyses of patient outcomes (duration of bowel rest, duration of antibiotics, time to full feeds) will follow the intention-to-treat principle, with statistical significance set at a P value of < 0.05.

28.2 We will use t-test to analyze differences in mean time of BUS image acquisition and reporting. Chi-square test will be used to compare differences in proportion of BUS studies that were performed and reported per standardized protocol. Inter-rater reliability for BUS studies will be assessed by Cohen's kappa statistics.

28.3 Sample size was calculated based on our pilot study which demonstrated a mean \pm SD of duration to full enteral feeds of 16 ± 9 days per episode of NEC concern. Using this information, we generated Table 1, which shows sample sizes for a range of possible means and standard deviations, with significance level of 0.05 and 80% power. For a 1-year study with 67 to 81 distinct episodes, for an SD of +8 days, we anticipate having sufficient sample size to detect a 5- to 6-day difference in mean duration to full feeds (highlighted in gray in Table 1).

Difference of means between groups	Expected Standard Deviation		
	± 8	± 9	± 10
4 days	126	160	198
5 days	81	102	126
6 days	56	72	88

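### In the BUS arm the post-AXR survey is answered knowing that BUS will follow, so the paired McNemar test in 28.1 cannot separate a BUS effect from anticipation, and the AXR-arm surveys that could help have no planned analysis

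*Combined protocol and SAP*

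**What the plan says.** Section 10.2 allocates infants by birth month, and the allocation is open: "A pre-generated randomization calendar will be posted in the NICU workroom to inform the care team which arm the infant will be randomized to". Section 10.3 then provides that "infants randomized to AXR + BUS intervention will have both a portable abdominal x-ray and add-on BUS ordered".

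Section 11.0 describes two surveys, both completed by the treating neonatologist on a 5-point likelihood scale. The first covers both arms: "The first survey (post-AXR survey), applicable to all infants, will be conducted after AXR is performed". The second covers one arm: "The second survey (post-BUS survey), applicable only to infants randomized to AXR + BUS, will be conducted after BUS is performed". The documents do not reproduce the survey items.

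Section 28.1 plans a two-tailed McNemar test with paired measures "to analyze differences in diagnostic thinking efficacy and therapeutic efficacy from pre- and post-BUS surveys". By protocol only BUS-arm infants have both surveys, so only that arm can contribute pairs. No analysis is stated for the AXR-arm post-AXR surveys. The intention-to-treat sentence in 28.1 names bowel rest, antibiotics and time to full feeds, and does not mention the surveys.

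**The concern.** The paired test reads the move from the first to the second survey as the effect of BUS. That needs the first rating to be what the clinician would think and plan on AXR alone. In the BUS arm it is given by someone who knows a second test is due. Such a clinician may stay uncommitted until BUS returns, or may rate treatment as likely for the time being and step down afterwards. Either movement would enter the test as change due to BUS, even if BUS added nothing to the decision that AXR alone would have produced. Completing the first survey before BUS is reported would not cure this, because the arm is already known.

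The AXR-arm neonatologists answer the same survey with no protocol BUS pending. Theirs is the concurrent randomised reference for the rating that is wanted, and the plan leaves it unused. What is at stake is the part of aim 1 that concerns differential diagnosis and therapy plan.

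**Working it through.** **The plan's own figure.** The only sizing is Table 1 in 28.3, for time to full feeds. With two-sided alpha 0.05, 80% power and 1:1 allocation, total N = 4 × [SD × (1.96 + 0.842) / difference]². For SD 8 and 5 days this is 4 × (8 × 2.802 / 5)² = 80.4, against 81 stated. The table reproduces as total sample sizes and is not in dispute. Nothing is sized for the surveys.

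**Inputs for the illustration.**
- Pairs: 40, half of the 80-infant target in Addendum B; or 100, half of the 200-neonate goal in section 8.0. The 1:1 ratio is an assumption.
- Share *a* of BUS-arm respondents who hold back at the first survey and revert at the second, all in one direction: not in the documents; 5% to 20% is shown.
- Random switching *r* each way: assumed 0 or 5%.
- The Likert answer is cut to yes/no. McNemar needs a cut-point, and the documents give none.
- BUS truly changes nothing.

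**Single-trial arithmetic.** With k discordant pairs all one way, exact McNemar P = 2 × 0.5^k. So k = 5 gives 0.0625, k = 6 gives 0.031 and k = 8 gives 0.008. Direction matters: 6 against 1 gives 2 × (1 + 7)/2⁷ = 0.125; 8 against 2 gives 2 × (1 + 10 + 45)/2¹⁰ = 0.11; 4 against 4 gives 1.

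**Chance of a significant result.** The number of discordant pairs is Binomial(n, a + 2r), and a share (a + r)/(a + 2r) of them move in the deferral direction. With r = 0 and n = 40 the test needs at least 6 such pairs, so at a = 15% the chance is Pr[Binomial(40, 0.15) ≥ 6] = 0.567.

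| Share deferring | 40 pairs, r = 0 | 40 pairs, r = 5% | 100 pairs, r = 0 | 100 pairs, r = 5% |
|---|---|---|---|---|
| 0% | 0% | 0.5% | 0% | 2% |
| 5% | 1% | 5% | 38% | 18% |
| 10% | 21% | 17% | 94% | 54% |
| 15% | 57% | 36% | >99% | 84% |
| 20% | 84% | 57% | >99% | 96% |

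In this model more enrolment makes the spurious signal more likely.

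**What a between-arm check can show.** With 50% positive in the AXR arm, the 95% CI half-width is 1.96 × √(2 × 0.5 × 0.5 / n): ±22 points at 40 per arm and ±14 at 100. Power to detect a 15-point difference in post-AXR ratings is 27% at 40 per arm and 57% at 100; 80% power needs about 170 per arm. These figures ignore clustering by birth month, repeat episodes and repeat respondents, so they are optimistic.

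**The case against.** Several objections stand and limit the point.

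- A reader might infer that clinicians do defer and that the change is therefore overstated. No section shows this. Size and direction are unknown, and because Addendum B describes NEC as an emergency that can worsen quickly, provisional treatment followed by step-down is as plausible as holding back. Movement in both directions largely cancels in McNemar's test. Nor do the documents show that therapy plan would be affected most.
- A reader might infer that the survey wording is at fault. The items are not reproduced, so a suitable instruction may already be there. The scale asks for likelihood rather than a committed decision, which may also make holding back less natural.
- A reader might infer that AXR and BUS are ordered at the same moment. Section 10.3 says that both are ordered, not when. The point does not need simultaneity, since the calendar already reveals the arm.
- A reader might want a rule that the paired change is not attributed to BUS if post-AXR ratings differ between arms. That is unsound. The check would usually miss a 15-point effect at 40 per arm. A difference could also be case mix, because inclusion under 10.1 depends on the neonatologist's decision to image while the arm is visible.
- Bowel rest, antibiotics and time to full feeds are compared between arms by intention to treat, and the sample size rests on time to full feeds. Those comparisons do not use the surveys.

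None of this makes the first BUS-arm rating a clean AXR-only baseline, or gives the AXR-arm surveys a use.

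**Conclusion.** The point holds as a risk of bias that the planned analysis cannot exclude, not as a demonstrated bias. From the documents: the BUS-arm respondent knows at the first survey that BUS will follow, the survey test is within that arm only, and no analysis uses the AXR-arm surveys. By assumption: that some respondents defer, how many, and in which direction. If BUS changed nothing and 15% of 40 deferred one way, the test would be significant in about 57% of trials (36% with 5% random switching each way). At 5% deferral with 40 pairs the effect on the test is negligible. The exposure is confined to the diagnostic-thinking and therapy-plan claims of aim 1, and it should be addressed because those claims currently rest on the paired test alone.

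**What to change.** In 28.1, add two between-arm comparisons of ratings already collected:

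- (a) the final rating, post-BUS in the BUS arm against post-AXR in the AXR arm, as the randomised estimate of the effect of BUS on diagnostic and therapeutic thinking;
- (b) the post-AXR rating between arms, as a check on anticipation.

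Report each as an estimate with a 95% CI that allows for birth-month allocation, repeat episodes and the same neonatologists answering repeatedly. Treat the paired McNemar result as descriptive. State in advance that a null result in (b) does not rule out anticipation, and that a difference does not by itself prove it.

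If the survey items do not already say so, word the post-AXR items in both arms as a rating on the clinical picture and AXR alone. Wording cannot be repaired once the surveys have been answered.

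The cost is slightly more analysis, wide intervals for the between-arm estimates, and an item that is hypothetical in the BUS arm. No new data collection or change in care is needed.

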12.0 Follow-up

- All study infants will be followed throughout their course in the NICU, from admission to discharge. All data will be collected through clinical chart review. Follow-up will end once infants are discharged from the NICU. We will collect the following data points: (1) baseline characteristics (gestational age, birth weight, sex, race, mode of delivery, Apgar scores; (2) clinical characteristics at time of NEC concern (clinical presentation, age at time of NEC concern, results of diagnostic tests for NEC concern, information on treatment including days to full enteral feeds and days on antibiotics); and clinical outcomes at discharge (total length of stay, age at discharge, co-morbidities during NICU admission).

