10.0 Procedures

10.1 Inclusion

Eligible infants who develop clinical concern for NEC for which the neonatologist decides to obtain imaging for further evaluation as part of usual clinical care will be included into the study.

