26.0 Data Collection*

26.1 The study will collect baseline clinical characteristics, lab test results, AXR and BUS results, clinical diagnosis, treatment data, and survey results.

- Clinical characteristics: gestational age at birth, weight at birth, sex, race/ethnicity, age at time of NEC concern,
- Lab test results: complete blood cell count (CBC), C-reactive protein (CRP), blood culture
- AXR and BUS results: time of order input in the chart, time of image acquisition, time of reporting, text of report and interpretation by radiologist
- Clinical diagnosis: NEC, no NEC, food protein-induced enterocolitis, clinical sepsis, other diagnosis

- Treatment data: medical treatment of NEC including days of bowel rest, days to full enteral feeds, days on antibiotics; surgical treatment of NEC including peritoneal drainage or exploratory laparotomy
- Survey results: post-AXR survey and post-BUS survey by neonatologists

26.2 Data will be obtained from the electronic medical record and surveys/questionnaires.

26.3 Sensitive Data: We will not be collecting or accessing sensitive data.

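### Feeding level before the NEC concern is not on the collection list, which gives up some precision on days to full feeds and leaves feeding stage at entry uncheckable between arms

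*Combined protocol and SAP*

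**What the plan says.** Two sections list the data to be collected. Section 12.0 names baseline characteristics, then "clinical characteristics at time of NEC concern (clinical presentation, age at time of NEC concern, results of diagnostic tests for NEC concern", then treatment information and outcomes at discharge. Section 26.1 gives the clinical characteristics as "gestational age at birth, weight at birth, sex, race/ethnicity, age at time of NEC concern". In 26.1 feeding appears only under treatment: "medical treatment of NEC including days of bowel rest, days to full enteral feeds, days on antibiotics". Section 12.0 gives the source: "All data will be collected through clinical chart review".

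Entry, in section 10.1, is for "Eligible infants who develop clinical concern for NEC for which the neonatologist decides to obtain imaging". No feeding condition is stated there. Section 10.2 sets the arm by calendar month of birth, from a schedule drawn up in advance and displayed on the unit. Section 10.7 keeps an infant in the same arm for any later episode.

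Section 28.3 sizes the trial on a pilot "duration to full enteral feeds of 16 ± 9 days per episode of NEC concern". Section 28.1 states: "Comparison of duration of antibiotics, bowel rest, and days to full enteral feeds will be performed using Student's t-test". It adds a Kaplan-Meier curve for time to full feeds. Neither analysis has a covariate.

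**The concern.** Some infants may be on full feeds when NEC is first suspected, and others may still be advancing. For the second group, days to full feeds could include advancement that would have been needed without any episode. If so, feeding stage predicts the outcome that sizes the trial, and the planned data set does not record it. Gestational age, birth weight and age at concern are only proxies.

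Two things are at stake. The first is precision: a prognostic factor that is not recorded cannot be used to reduce residual variance. The second is a check on who enters. The arm can be known from the birth month before the neonatologist decides whether to image, and that decision brings the infant into the trial. If the threshold for imaging differed by arm, feeding stage at entry could differ too. The documents do not show that this will happen, but the listed data would not reveal it.

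**Working it through.** **1. The plan's own figure.** For a two-sided 5% level (assumed for the t-test, since two-tailed is written only for McNemar's test), 80% power and equal arms, total N = 4 × (2.80 × SD / difference)². For SD 8 and 5 days this gives 80.4 with unrounded normal quantiles. Table 1 states 81. The other eight cells also reproduce as totals, so the sample-size arithmetic is not in question.

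**2. Detectable difference at the pilot SD.** With SD 9 and 81 episodes: 2.80 × 9 × 2/√81 = 5.6 days.

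**3. Assumptions.** The documents do not give the share of episodes that start before full feeds (p) or the extra days those episodes take (d). Three illustrative pairs are used. The total SD is held at 9, which treats the pilot SD as already containing the mixture, and episodes are treated as independent.

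- SD due to feeding stage = d × √(p(1−p))
- Residual SD = √(81 − d² × p(1−p))
- Detectable difference = 2.80 × residual SD × 2/√81
- One-standard-error chance imbalance = d × √(p(1−p) × (1/40 + 1/41))

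| p, d | SD from feeding stage | Residual SD | Detectable difference | One-SE imbalance |
|---|---|---|---|---|
| 30%, 5 days | 2.3 | 8.7 | 5.4 days | 0.5 days |
| 40%, 7 days | 3.4 | 8.3 | 5.2 days | 0.8 days |
| 50%, 10 days | 5.0 | 7.5 | 4.7 days | 1.1 days |

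**4. A wider range.** With p from 25% to 75% and d from 4 to 10 days, feeding stage would explain about 4% to 31% of the variance. Power for a 5-day difference with 81 episodes would rise from 70.5% to between 72% and 85%. The 95% range of the chance shift would be about ±0.8 to ±2.2 days.

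**5. Scale of the imbalance.** The standard error of the arm difference at SD 9 is 9 × 2/√81 = 2.0 days. The 0.5 to 1.1 days in step 3 is part of that 2.0, not an addition to it. Allocation by birth month could make imbalance larger than independent episodes would give; this was not quantified.

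**The case against.** The strongest case against has five parts.

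- **The lists are broad categories.** Clinical presentation at the time of concern is on the list and could include feeding status. The case report form is not supplied. The text reviewed shows no sections 4.0 to 7.0 and no detailed eligibility list, so a feeding condition may exist elsewhere. This stands as a limit: the share of infants not yet on full feeds is unknown. Still, nothing in the lists says that presentation covers feeding level.
- **The mechanism is assumed.** The plan records bowel rest. If feeds are stopped and restarted, infants previously on full feeds must re-advance too. This also stands; the extra 5 to 10 days are illustrative.
- **The context is thin.** A reader might infer from Addendum B, item 3, that many episodes precede full feeds. That remark concerns pilot infants whose families could not be approached for consent. Early in a hospital stay after transfer is not early in life. The justification for including neonates, ahead of section 8.0, puts peak onset at roughly weeks 2 to 4, but it does not say who was on full feeds.
- **The effect is modest.** In two of the three scenarios the detectable difference falls by only 0.2 or 0.4 days. With the 200 neonates of section 8.0, taken as independent episodes, the one-standard-error imbalance would be about 0.3 to 0.7 days.
- **The information is not lost.** A reader might infer that recovery and ordinary advancement can never be told apart. That describes the planned data set, not the chart from which it is drawn.

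What remains is that a plausible prognostic factor for the outcome that sizes the trial is not named, and that adding it is easy.

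**Conclusion.** The omission is real and worth correcting, but its consequence is limited. It forgoes precision of unknown size: 5.6 days detectable becomes 5.4 to 4.7 under the assumed shares and extra days, an SD of 9 and 81 independent episodes. It also removes a check on whether the arms enter at the same feeding stage, which matters because the arm is knowable before the decision to image.

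Two stronger conclusions are tempting, and the documents support neither. A reader might infer that the comparison is biased. Mixed feeding stage affects both arms, and its chance imbalance is already in the t-test's standard error. A systematic difference would need entry to depend on arm, which is possible but not shown. A reader might also infer that the sample size is wrong. The pilot SD of 9 may already contain this mixture, and Table 1 reproduces. Nor is feeding level a baseline value of the outcome: days to full feeds is a duration counted after the concern, so the earlier level is a covariate.

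**What to change.** - **Section 26.1:** for each episode, add the enteral feed volume in the 24 hours before the NEC concern and whether full feeds had been reached (yes/no), both abstracted from the chart. Use the same definition of full feeds as for the outcome; none appears in the text reviewed.
- **Section 28.1:** tabulate both items by arm. Add a prespecified regression of days to full feeds on arm, with the value before the infant's first episode as covariate.
- **Later episodes:** do not adjust for feeding level before a second or later episode. Infants keep their arm (section 10.7), so that level may already be affected by the imaging assigned in the first episode.
- **Results by feeding status:** report as descriptive only. About 81 episodes cannot support more.

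The cost is slightly more chart abstraction and one regression in addition to the planned t-test. Clinical care does not change. Prespecifying the covariate matters, because adjustment chosen after the results are seen is less credible.

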13.0 Genetic Analysis Information - NA

14.0 Sharing of Results with Participants

14.1 Results of all AXR and BUS will be uploaded in the electronic medical record as per usual standard workflow for any imaging test ordered in clinical practice. These results will be accessible by

SHORT TITLE: BUS for NEC

neonatologists, radiologists, and other members of the clinical team authorized to view the infant's clinical chart as part of their duties in taking care of the infants in the study. Parents who are enrolled in the patient portal at CMH or KUMC will also have access to these results, just as they have access to all other results and health information of their infant.

